Sedentary behavior (average min/day)	Primary	Week 0 (baseline); Week 3; Week 6; 3 Months	This metric quantifies the change in the average amount of time spent sedentary each day, from the baseline, Week 2, Week 6, and 3-month periods. It is a marker of time spent inactive.
Moderate-vigorous activity (average min/day)	Secondary	Week 0 (baseline); Week 3; Week 6; 3 Months	This metric quantifies the change in the average amount of time spent engaged in moderate-to- vigorous physical activity each day,

			from the baseline, Week 2, Week 6, and 3-month periods. It is a marker of physical activity.
Walking Cadence	Secondary	Week 0 (baseline); Week 3; Week 6; 3 Months	This metric reflects the participant's average steps per minute. We will examine change from baseline over the course of the intervention and follow-up.
Walking Bouts	Secondary	Week 0 (baseline); Week 3; Week 6; 3 Months	This measures the number of 'bouts' of physical activity (in our case, steps). We will have two counts: the number of 5+ minute bouts and the number of 10+ minute bouts of walking. We will examine change from baseline over the course of the intervention and follow-up.

A spreadsheet holding the list of neuropsychological assessments to be used, with brief descriptions, is attached. They will be administered at T1 (Week 0), T2 (Week 1), T3 (Week 6), and/or T4 (3 Months).

		6 weeks of daily messages								
(soon after phone screen)	Week 0/ Start	1	2	3	4	5	6	7	14/ 3 months	15
	(shipping)	Devices			Devices			Devices	>>>	Devices
Consent Visit	Visit 1	Visit 2		Phone Reminder			Visit 3	Phone Reminder	Visit 4	Debrief
Remote Visit	Remote Visit	Remote Visit					Remote Visit	Phone Reminder	Remote Visit	Debrief
		Optional MRI					Optional MRI			

Who will conduct the experimental procedures, questionnaires, etc.? Where will this be done? *Attach copies of all questionnaires, interview questions, tests, survey instruments, links to online surveys, etc.*

Most research activities are remote and will be completed by participants in their homes. Optional MRIs occur in the Center for Cognitive & Brain Health in the ISEC on the Northeastern University Boston campus. As indicated above, all experimental procedures will be implemented and monitored by trained staff in the Lab. All questionnaires, surveys, etc. are attached.

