17 NCT04315363
18
19 March 6 2021
20
21
22
23
24
25
26
27
28
29
30
31
32
33
34
35
36
37
38
39
40
41
42
43
44
45
46

47 **Abstract**

48
49 Sedentary behavior increases the risk for multiple chronic diseases, early mortality, and
50 accelerated cognitive decline in older adults. Interventions to reduce sedentary behavior among
51 older adults are needed to improve health outcomes and reduce the burden on healthcare
52 systems. We designed a randomized controlled trial that uses a self-affirmation manipulation and
53 gain-framed health messaging to effectively reduce sedentary behavior in older adults. This
54 message-based intervention lasts 4 weeks, recruiting 80 healthy but sedentary older adults from
55 the community, between the ages of 60 and 95 years. Participants are randomly assigned to one
56 of two groups: 1) an intervention group, which receives self-affirmation followed by gain-framed
57 health messages daily or 2) a control group, which receives daily loss-framed health messages
58 only. Objective physical activity engagement is measured by accelerometers. Accelerometers are
59 deployed a week before, during, and the last week of intervention to examine potential changes
60 in sedentary time and physical activity engagement. This study will assess the effectiveness of a
61 novel behavioral intervention at reducing sedentarism in older adults and examine the
62 neurobehavioral mechanisms underlying any such changes.

63
64 **Keywords:** sedentary behavior, randomized controlled trial, self-affirmation, positive
65 messaging, affective psychology, fMRI

66 **Introduction**

67 Sedentarism is an epidemic among older adults, given that they spend an average of over 8 hours
68 being sedentary daily [1,2]. Moreover, physical inactivity has increased sharply during the
69 COVID-19 pandemic [3]. The potential health risks of leading a sedentary lifestyle are well
70 established. Time spent sedentary (as measured by metabolic equivalents of task (MET) ≤ 1.5
71 [4]), is positively associated with increased risk for all-cause mortality, cardiovascular disease,
72 cancer, and type 2 diabetes [5,6] and negatively associated with cognitive status in later life
73 [7,8]. Moreover, physical inactivity costs healthcare systems approximately 53.8 billion
74 international dollars each year [9]. Consequently, developing effective strategies to motivate
75 reductions in sedentary time in older adults will significantly improve their health and well-

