272 server, a cloud-based system that sends and receives hash-encrypted links. Collected anonymized
273 data are stored on the messaging site behind an administrative login on the Heroku server.

274

275 *Analysis plan*

276

277 Power calculations were performed to statistically determine the target sample size of
278 N=80 for this pilot study. The power is calculated in R based on a two-sample T-test model with
279 our primary outcome, the percent of daily sedentary time assessed using an activPAL. We
280 expected a similar baseline sedentary sample to the study by Falk et al., where participants were
281 sedentary an average of $50.6\% \pm 14.0\%$ of their time [11]. Our proposed sample size of 80
282 participants (40 per group) will allow us to detect a minimum detectable difference of 10.0%
283 between the two groups (i.e., the group difference in averaged sedentary time/total valid awake
284 time) at week 4 post intervention with a common standard deviation of 14.0% with 80% power
285 and a two-sided alpha of 0.05, with 20% drop-out rate accounted. We expect that the ratio of
286 sedentary time/total valid awake time in the self-affirmation + positive framing group will be
287 10.0% less than the control negative framing group, based on our power analysis.

288 After compiling all data across the 3 different data servers, data will be checked for
289 completeness and correctness using frequency distributions (for missing data and out-of-range
290 values). Group differences at baseline are examined for variables including demographic factors
291 (i.e., age, sex, educational level, socioeconomic status, race/ethnicity), baseline sedentary time,
292 self-report sitting time, in order to detect potential confounding factors. For the primary
293 hypothesis that self-affirmation + gain-framed messages decrease sedentary time more so than
294 loss-framed messages, and the secondary outcome of increased MVPA after the intervention, all
295 outcome measures about sedentary behavior and MVPA are first quantified using available
296 software. Changes in sedentary behavior (% daily sitting and lying time, minutes/per day in

297 physical activity) over time (3 time points) are analyzed using linear mixed effect models to
298 account for the correlated data and likely heterogeneous variability. These models will include a
299 random intercept and slope to account for subject-specific changes as well as a group (2) x time

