300 (3) interaction fixed effect. This allows for modelling of the effect of our intervention as a
301 function of both group and time as well as accounting for potential confounding covariates. All
302 model assumptions will be tested both visually and formally and associations between covariates
303 will be assessed to protect against multicollinearity. All valid data are included in the model
304 initially, followed by per protocol analyses, in which the cases with (1) less than 4 valid days of
305 ActiGraph or (2) less than 5 valid days of activPAL or (3) more than 2 days with non-
306 compliance of daily message intervention are excluded in the analysis. For the final dataset, the
307 multiple imputation by chained equations (MICE) will be used for imputing missing values with
308 10 imputations.

309

310 Discussion

311

312 Efficacious behavioral interventions to decrease sedentary behaviors in older adults will
313 have a critical impact on disease prevention, quality of life and public health. The COVID-19
314 pandemic has further heightened the urgency to reduce sedentary due to increased inactivity
315 among older adults [3]. We have designed a 6-week pilot randomized controlled trial to examine
316 the efficacy of daily self-affirmation and gain-framed messaging in decreasing sedentary time.
317 Through increasing receptivity to health messages via reinforcement of self-referential and
318 positive valuation networks, we hypothesize there will be a significant reduction in sedentary
319 time in the intervention group, compared to the control group (who receives loss-framed
320 messages only).

321 There are several notable limitations to this study, yet we have taken a number of
322 measures to minimize their impact. First, this is a pilot study with only a moderate sample size.
323 Nevertheless, a power analysis of our primary outcome measure was performed to ensure that a
324 sample size of 80 is sufficient to detect a true effect with 80% power. Additionally,
325 interpretations of individual component contributions of our intervention are to be taken with
326 caution given we cannot disentangle the effect of gain-framed messaging from self-affirmation.
327 Regarding the inclinometer and accelerometer-based assessments, we are limited to the
328 collection of data for 3 periods of 1 week (i.e., not assessing accelerometry throughout the entire

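### The SAP does not say which contrast of its group-by-time mixed model decides the primary hypothesis, and its 80% power belongs to only one of the candidates

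*SAP*

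**What the plan says.** All of the statistical text is in the SAP's Analysis plan.

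- **Power.** "The power is calculated in R based on a two-sample T-test model with" percent daily sedentary time on the activPAL as the outcome. The powered quantity is a minimum detectable difference of 10.0% "between the two groups (i.e., the group difference in averaged sedentary time/total valid awake" "time) at week 4 post intervention with a common standard deviation of 14.0% with 80% power", with two-sided alpha 0.05, 40 per group and 20% drop-out allowed for.
- **Hypothesis.** The primary hypothesis is stated comparatively: the "hypothesis that self-affirmation + gain-framed messages decrease sedentary time more so than" the loss-framed control.
- **Analysis.** Changes over three time points are analysed by linear mixed effect models with a "random intercept and slope to account for subject-specific changes as well as a group (2) x time" ("3) interaction fixed effect. This allows for modelling of the effect of our intervention as a" function of group and time). Possible confounders may be added. The Abstract places the sensors as "deployed a week before, during, and the last week of intervention to examine potential changes", so the three time points appear to be baseline, mid-intervention and the last intervention week.

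No sentence in either document names the coefficient, contrast or joint test that decides the primary hypothesis. No within-person correlation is given. The SAP's Discussion nevertheless says, without qualification, that 80 participants are enough for 80% power.

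The Protocol's outcome table (section J) lists two primary outcomes, total step count and sedentary minutes per day. It describes the latter as "change in the average amount of time spent sedentary each day, from the baseline", and the sentence then runs on to Week 2, Week 6 and 3-month periods.

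**The concern.** The power paragraph and the analysis paragraph describe different things. The first concerns a level difference at one week. The second concerns change over time and names only a group-by-time interaction. A three-level interaction has two degrees of freedom, and the same model can also yield a final-week difference, a baseline-to-final change, a mid-week contrast or, with baseline handled suitably, an adjusted final-week difference.

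Under randomisation the final-week, change and baseline-adjusted contrasts target the same effect, but with different precision. The joint interaction test also responds to the mid-week pattern. Two things follow. The stated 80% cannot be attached to the primary test until that test is named. And the choice among the candidates could be made after the results are known.

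**Working it through.** **Inputs from the SAP's Analysis plan:** difference 10 points, SD 14, two-sided alpha 0.05, 40 per arm, 20% drop-out. Evaluable per arm: 40 × 0.8 = 32.

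**Inputs that the documents do not give, assumed here:** the baseline-to-final correlation *r* (shown at 0.3, 0.5, 0.7); SD 14 at every sensor week; for the interaction only, compound symmetry and a 5-point mid-week effect. Complete cases are used, and the planned multiple imputation is not modelled.

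**1. The plan's own figure.** The standard error of a difference in means is SD × √(2/32) = SD × 0.25. With SD 14 it is 3.5, so the noncentrality is 10/3.5 = 2.857. On 62 degrees of freedom, power is 80.3% and the minimum detectable difference is 9.96 points. The stated figure reproduces, and it does not depend on *r*.

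**2. Change from baseline to the final week.** SD of change = 14√(2(1−*r*)).

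| *r* | SD of change | Noncentrality (40/SD) | Power |
|---|---|---|---|
| 0.3 | 16.57 | 2.41 | 66% |
| 0.5 | 14.00 | 2.86 | 80% |
| 0.7 | 10.84 | 3.69 | 95% |

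This equals the powered t-test only where 2(1−*r*) = 1, that is *r* = 0.5. Below that it is less precise, and above it more precise.

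**3. Baseline-adjusted final week.** Residual SD = 14√(1−*r*²), on 61 degrees of freedom.

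| *r* | Residual SD | Noncentrality (40/SD) | Power |
|---|---|---|---|
| 0.3 | 13.36 | 3.00 | 84% |
| 0.5 | 12.12 | 3.30 | 90% |
| 0.7 | 10.00 | 4.00 | 98% |

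Because 1−*r*² never exceeds 1, this is at least as precise as the unadjusted comparison. Because 1−*r*² = (1−*r*)(1+*r*) never exceeds 2(1−*r*), it is also at least as precise as the change contrast. Both statements hold up to a negligible loss of degrees of freedom; at *r* = 0 power is still 80.3%.

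**4. Two-degree-of-freedom interaction.** Between-arm effects are 0, 5 and 10 points at the three weeks, so the two change contrasts are 5 and 10. Under compound symmetry each arm's change covariance is 196(1−*r*) × [[2, 1], [1, 2]]. The quadratic form is (2×25 − 2×50 + 2×100)/3 = 50. The noncentrality is (32/2) × 50/(196(1−*r*)) = 4.08/(1−*r*), referred to F(2, 61).

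| *r* | Noncentrality | Power |
|---|---|---|
| 0.3 | 5.83 | 55% |
| 0.5 | 8.16 | 70% |
| 0.7 | 13.61 | 91% |

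Steps 2 and 3 need only *r* and equal SDs. Step 4 also depends on the covariance shape and the mid-week effect: with effects of 0, 10 and 10 points the same test has 68, 83 and 97% power.

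**The case against.** The strongest reply is that the power paragraph already shows the intent. It gives one between-group quantity a time point, a size, an alpha and an expected direction. The mixed model can estimate that quantity, and for it the 80% stands. Planning with a simple t-test and analysing with a richer model is ordinary practice, and the SAP's Study aims call this a Stage I pilot.

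Much of that is fair. The power paragraph does suggest the final-week difference, and what is missing may be one linking sentence. But a suggestion in the sample-size text is not a pre-specified test when the analysis text speaks of changes and names only the interaction. The pilot label does not remove the need either, because the SAP states a primary hypothesis, aims to test efficacy and claims 80% power for it.

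Two stronger readings should be resisted. A reader might infer that the trial is underpowered. The documents do not support this: every figure below 80% rests on an assumed correlation, covariance shape or mid-week effect, and other plausible values give more than 80%. A reader might also infer that the Protocol fixes change from baseline as the outcome. Its sentence lists several periods after baseline, is not clearly a definition of change from baseline, and is in minutes per day rather than percent of waking time. The support for a change reading comes mainly from the SAP's own hypothesis and model wording.

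**Conclusion.** The concern holds as one of specification. The 80% power is correct for an unadjusted final-week comparison; the analysis assigned to the primary hypothesis does not commit to that comparison or to any other. For one and the same 10-point final effect, the three alternatives worked out above run from 55% to 98% power over correlations of 0.3 to 0.7, on both sides of the stated figure. The sample size, SD, effect and drop-out behind those numbers are the SAP's; the correlation, equal SDs, covariance shape and mid-week effect are assumptions. The absence of a named deciding contrast depends on none of them. It should be corrected, and a better contrast is available at no cost in data.

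**What to change.** In the SAP's Analysis plan:

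- Name one deciding test: the between-arm difference in percent waking sedentary time in the end-of-intervention sensor week, at two-sided alpha 0.05. Take it from the planned mixed model with categorical time and baseline means constrained equal across arms. The alternative is baseline as a covariate, in which case baseline must leave the outcome vector. Choose one of the two in advance.
- Make the omnibus interaction and the mid-week contrast secondary.
- State that 80% is the power of the unadjusted final-week comparison, and so an approximate lower figure for the adjusted contrast, or restate power over a declared range of correlations.

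Two reconciliations belong with this. The Protocol's outcome table makes both step count and sedentary minutes per day primary, which does not match a single primary test on percent of waking time. The final sensor week is called week 4 in the SAP's power paragraph but week 6, between T3 and T4, under Physical activity monitoring.

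The cost is about a paragraph of SAP wording, a sentence on power, and aligning the Protocol table and the week label. No new data are needed, because baseline is already collected.

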128 The DASH study is a stratified block randomized controlled trial. After reading and signing informed consent, recruited participants are randomized to either a self-affirmation plus gain-framed daily messaging group (intervention) or a loss-framed daily messaging only group (control) with a ratio of 1:1. Due to the constraints of in-person assessment during the COVID-19 pandemic, onsite participation in the MRI scans before and after the intervention is optional. Therefore, we stratify the randomization by MRI participation (yes/no) to ensure the same distribution of MRI and behavioral-only participants across the two groups. Loss-framed messages were chosen as a control group (over neutral messaging) as they provide the same contextual information as the gain-framed messages (only framed in a negative way), compared

139 to neutral messages which contain factual information (see Figure 3B for an example of gain-
140 versus loss-framed messages). All participants are informed about the randomization but blinded
141 to the group assignment. Participants are informed that the study aims to examine whether a 4-
142 week program promotes brain health and behavior. However, it is not possible to blind
143 experimenters, as they view the intervention related materials and give instructions during the
144 assessments. The randomization scheme is prepared by the Harvard Catalyst Biostatistical Group
145 using a stratified permuted block method with random blocks. All experimenters are blinded to
146 the block size. Sealed envelopes are provided to the investigator and stored at the designated site.
147 This trial is registered on clinicaltrials.gov with an identifier NCT04315363. This study received
148 ethical approval from Northeastern University Institutional Review Board (IRB).
149

150 **Participants**

151
152 We plan to recruit 80 sedentary older adults for this study between the ages of 60 and 95
153 years that engage in less than 150 minutes of moderate-to-vigorous-intensity aerobic exercise per
154 week and more than 8 hours of sitting time per day, as assessed with a self-report during an
155 initial phone screening. We plan to recruit a diverse population that is balanced across race, sex,
156 and socioeconomic status. The study is advertised via promotional flyers in and around the
157 Boston area and local senior citizen centers as well as online advertisements through websites

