214 throughout the intervention. During weeks 3 and 6, they also receive daily reminders to continue
215 wearing their accelerometers. This daily message survey setup is displayed in Figure 2. The
216 researcher's contact information is displayed on each survey page to enhance compliance. To
217 monitor the participation adherence, participants' responses are tracked and those that do not
218 complete the survey by a specified time of day are contacted the following day by research
219 assistants to prevent technical failures. The time spent on the daily message intervention
220 including the healthy messages and survey questions is recorded by the daily message system, no
221 response to the survey questions or responses under 3 seconds to the self-affirmation probe are
222 considered as non-compliance.

223
224 **Figure 2.** Messaging system setup and logic. Each participant (represented by P_x , where x designates the
225 participant number) receives their unique link. In that link, they follow a series of pages each day that
226 contains their unique questions and parameters based upon the inputted comma-separated values (CSV)
227 file. The system does not initiate until the participant begins on their first day and then repeats for 42 days
228 (4 weeks) for the duration of the daily messaging intervention. The process occurs synonymously for all
229 other participants. Links that are not activated simply remain idle until a participant is assigned that link
230

231 Measurements and materials

233 Physical activity monitoring

234 Time spent sedentary as the primary outcome will be measured with an activPAL
235 inclinometer (activPAL, PAL Technologies, Glasgow, UK). Sleep quality, duration, and physical
236 activity engagement will be measured as secondary outcomes using an GT9X Link
237 accelerometer (ActiGraph LLC, Pensacola, FL). Participants will be wearing two motion sensors
238 at week 0 (between T1 and T2), week 3 (mid-intervention), week 6 (between T3 and T4) and
239 week 14 (T5), 24 hours/day for seven continuous days (see Figure 1). To measure sedentary
240 time, an activPAL monitor is attached on the mid-anterior surface of the right thigh. This device
241 is used to measure postural aspects of sedentary behavior, including time spent lying and sitting,
242 standing, and the number of sit-to-stand transitions. An accelerometer will be worn on the non-

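### The random intercept and slope are under-specified: one reading is not identifiable, the other can misstate visit-specific standard errors in either direction; an unstructured 3x3 covariance avoids both at small cost

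*SAP*

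**What the plan says.** The SAP analysis plan uses linear mixed models on three time points. The stated purpose is to "account for the correlated data and likely heterogeneous variability. These models will include a" "random intercept and slope to account for subject-specific changes as well as a group (2) x time" (3) fixed interaction. Time is therefore a three-level factor in the fixed part. Five things are not stated: whether the random slope is on that factor or on numeric weeks, the residual structure, the degrees-of-freedom method, which group-by-time contrast is primary, and what is fitted if the model does not converge. Model assumptions are to be checked, but no alternative covariance is named.

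The time scores are not settled either. The SAP section on physical activity monitoring puts the sensors "at week 0 (between T1 and T2), week 3 (mid-intervention), week 6 (between T3 and T4) and" week 14. The SAP abstract and study timeline describe a 4-week intervention, with sensors in week 3 and the last week. The caption of SAP Figure 2 equates 42 days with 4 weeks, and the Discussion uses both 6 weeks and 4 weeks. The protocol has six weeks of messages. The powered comparison is a group difference "time) at week 4 post intervention with a common standard deviation of 14.0% with 80% power".

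**The concern.** With only three observations per person, the covariance model largely determines the standard error of each visit-specific contrast. Here two analysts could follow the text faithfully and fit different models, one of which has no unique solution. The other treats the step from the pre-message week to mid-intervention as exactly as variable as the step between two weeks under messaging (on equal spacing). Nothing in the design supports that equality. At stake are the intervals for the individual weeks, and a covariance choice made after the data are seen if the first fit is singular or fails.

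**Working it through.** **Inputs.** From the SAP analysis plan: SD 14.0, difference 10.0, 40 per arm, 20% dropout, two-sided 0.05. Assumed here, because the documents give none: correlations between weeks, written baseline–mid / baseline–last / mid–last, and any unequal SDs.

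**1. The plan's own figure.** A two-sample t-test with difference 10 and SD 14 has power 79.0% at 31 per arm and 80.3% at 32. Then 32/0.8 = 40 per arm, total 80. The plan's N is reproduced.

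**2. Identifiability.** A 3x3 covariance has 6 distinct elements.
- Slope on the factor: 3 random effects (6 parameters) + 1 residual variance = 7 parameters; Jacobian rank 6. Not identified.
- Slope on numeric weeks: 3 + 1 = 4 parameters; rank 4 on scores 0/3/6 and on 0/3/4. Identified, with 6 − 4 = 2 restrictions.

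**3. What the restriction does on 0/3/6.** Let L = last − baseline and Q = baseline − 2·mid + last. The model forces Cov(L, Q) = 0. Write D1 = Var(mid − baseline) and D2 = Var(last − mid). The model replaces both by (D1 + D2)/2. Var(L) stays free as long as the random-effects covariance is inside its bounds; in particular the slope variance must be positive, which requires Var(L) > Var(Q)/3.

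With SD 14, 2 × 14² = 392:
- .5/.5/.8: D1 = 392 × 0.5 = 196; D2 = 392 × 0.2 = 78.4; mean 137.2. SE ratio (model/true) = √(137.2/196) = 0.837.
- .6/.6/.75: D1 = 156.8; D2 = 98; mean 127.4. Ratio = √(127.4/156.8) = 0.901.
- .8/.5/.6: D1 = 78.4; D2 = 156.8; mean 117.6. Ratio = √(117.6/78.4) = 1.225.
- Compound symmetry or AR(1): D1 = D2, so the ratio is 1.

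In these cases the last-week ratio is 1. It departs from 1 when the slope variance is driven to zero. With SDs 12/16/12 and r = .7, Var(L) = 86.4 is below Var(Q)/3 = 438.4/3 = 146.1. The residual variance is then (86.4/2 + 438.4/6)/2 = 58.1, and the last-week ratio is √(2 × 58.1/86.4) = 1.160.

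**4. Scores 0/3/4.** The free contrast is (−7, 2, 5), the residual one (1, −4, 3). Mid change = (3 × first − 5 × second)/26; last change = (2 × first + second)/13. For .8/.5/.6 the two variances are 32.6 and 8.2 times 196.
- Mid: √[(9 × 32.6 + 25 × 8.2)/676 ÷ 0.4] = 1.358.
- Last: √[(4 × 32.6 + 8.2)/169 ÷ 1.0] = 0.906.

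**5. Results.** Type I error = 2·P(t62 > 1.999 × ratio), taking 32 per arm, in brackets.

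| Assumed truth | Scores | Week-3 change | Last-week change |
|---|---|---|---|
| Compound symmetry | either | 1.00 (.050) | 1.00 (.050) |
| AR(1), .7 | 0/3/6 | 1.00 (.050) | 1.00 (.050) |
| AR(1), .7 | 0/3/4 | 1.117 (.029) | 0.960 (.060) |
| .5/.5/.8 | 0/3/6 | 0.837 (.099) | 1.00 (.050) |
| .5/.5/.8 | 0/3/4 | 0.902 (.076) | 1.049 (.040) |
| .6/.6/.75 | 0/3/6 | 0.901 (.076) | 1.00 (.050) |
| .8/.5/.6 | 0/3/6 | 1.225 (.017) | 1.00 (.050) |
| .8/.5/.6 | 0/3/4 | 1.358 (.009) | 0.906 (.075) |
| SDs 12/16/12, r = .7 | 0/3/6 | 0.941 (.065) | 1.160 (.024) |

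One equal-SD pattern also moves the last-week SE on 0/3/6. With .5/.7/.5, where baseline resembles the last week more than the middle one, the slope variance is zero and the ratio is 1.202.

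**6. Overall test.** The large-sample type I error of the 2-df group-by-time test is 0.050 to 0.058 across the truths and both schedules.

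**7. Simulation.** 40 per arm, 20% monotone dropout, 800 runs, scores equally spaced; Monte Carlo SE √(.05 × .95/800) = 0.008. Entries are type I error for intercept-and-slope versus unstructured.
- .5/.5/.8: week 3, 0.102 versus 0.060; last week, 0.045 versus 0.046.
- AR(1) .7: 0.054 versus 0.060; 0.059 versus 0.059.
- Compound symmetry .6: 0.048 versus 0.049; 0.042 versus 0.046.

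**8. Cost of the unstructured model.** 6 parameters against 4. With 32 per arm, power is 80.3% (62 df) against 80.9% if the variance is pooled over time (124 df): 0.6 points.

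**The case against.** The best defence is that what the SAP actually names is barely affected. It specifies the group-by-time interaction, and the 2-df test of that interaction holds at 0.050 to 0.058. It powers an end-of-intervention comparison, and the last-week SE is exact on 0/3/6 in most equal-SD patterns. No week-3 contrast is designated. A random intercept and slope is a mainstream choice, the numeric-week reading is the more usual one, and this is a pilot. All of that stands, and it limits the point to visit-specific estimates and prespecification.

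A reader might infer more than the documents support:
- *That the model is unidentifiable outright.* Only the factor-slope reading is.
- *That week-3 intervals will be too narrow.* This needs the two messaging weeks to correlate more with each other than the baseline and mid-intervention weeks do. The documents give no correlations, and other patterns make the intervals too wide.
- *That the structure cannot represent unequal variances.* It can: with true variances 144/196/256 (r = .7), the fitted ones are about 150/196/250. What it restricts is the joint pattern of variances and covariances.
- *That singular fits damage inference.* Compound symmetry lies exactly on the slope-variance boundary, and 52–57% of 500 simulated fits were singular at correlation 0.6. Yet type I error there was 0.048 and 0.042. The difficulty is the missing fallback rule.
- *That the alternative is free.* It costs a little, as shown.

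**Conclusion.** The point holds as a prespecification gap with a bounded numerical consequence. The text admits one model with no unique solution and one whose visit-specific SEs depend on unstated time scores and an untested covariance restriction. In the truths tried, the week-3 change SE was from 16% too small to 22% too large on 0/3/6, and from 10% too small to 36% too large on 0/3/4. The last-week SE was right on 0/3/6 with equal SDs apart from the one boundary pattern (20% too large). It was 16% too large with SDs 12/16/12, and on 0/3/4 it could be 9% too small. These sizes rest on assumed correlations and SDs; only SD 14.0 comes from the SAP. There is no error under compound symmetry or equally spaced AR(1), and the overall interaction test and the N=80 calculation are not undermined.

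**What to change.** In the SAP analysis plan, replace the random intercept and slope with a repeated-measures mixed model: week as a three-level factor crossed with group, an unstructured 3x3 within-participant covariance, REML, and Kenward-Roger or Satterthwaite degrees of freedom. Name the fallback in advance, for example heterogeneous Toeplitz, with the rule that triggers it. State which group-by-time contrast is primary.

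This model needs no numeric time scores, but the sensor-week and intervention-length statements in the two documents still have to be reconciled so that the last analysed week is unambiguous.

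The cost is SAP wording and a small change of code, two more covariance parameters (estimable from 64 to 80 people) and about 0.6 points of power. Design and sample size do not change.
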